7.1 Primary Analysis Set (PAS)

This dataset consists of all enrolled subjects who received at least one infusion of blinatumomab. Primary analysis will be performed when all the enrolled subjects have finished at least 2 cycles of blinatumomab and the safety follow-up visit (if subjects discontinue treatment after 2 cycles), or have discontinued the treatment of blinatumomab and complete the safety follow up visit, whichever occurs first.

7.2 Safety Analysis Set (SAS)

All enrolled subjects who received at least one infusion of blinatumomab. The definition is the same as PAS.

7.3 Pharmacokinetic Analysis Set (PKS)

All subjects who received any infusion of blinatumomab and had at least one PK sample collected will be included in the Pharmacokinetic Analysis Set. These subjects will be evaluated for pharmacokinetics unless significant protocol deviations affect the data analysis or if key dosing, dosing interruption, or sampling information is missing.

7.4 Interim Analyses Set

The Interim Analysis Set is defined as the first 90 subjects (75% of the expected total) who have had the opportunity to be treated with at least 2 cycles of blinatumomab and to finish the safety follow-up visit (if subjects discontinue treatment after 2 cycles), or have discontinued the treatment of blinatumomab and complete the safety follow-up visit, whichever occurs first. The interim analysis will assess blinatumomab efficacy and safety and will be based on this Interim Analysis Set.

7.5 Subgroup Analyses

Subgroup analyses will be performed to explore the consistency of the treatment effect. This includes logistic regression or Cox regression that will estimate odds ratio or hazard ratio and its corresponding 95% confidence interval for treatment effect between subgroups. The following covariates may be used to examine efficacy and/or safety in subgroups or covariates analyses:

- Sex (female vs. male)
- Age (< 35 vs ≥ 35 to < 55 vs ≥ 55)
- Prior salvage therapy (yes vs. no)
- Prior alloHSCT (yes vs. no)
- Bone marrow blast at baseline (<50% vs. ≥50%)
- Disease status (primary refractory vs first relapse vs second or later relapse)
- Refractory to last previous therapy (yes vs. no)

8. Planned Analyses

8.1 Interim Analysis and Early Stopping Guidelines

The interim analysis will assess blinatumomab efficacy and safety and will be based on the Interim Analysis Set. The efficacious benefit assessment will be based on an O'Brien-Fleming alpha spending function (O'Brien and Fleming, 1979) with the critical boundary 42.2% at the interim analysis and 39.2% at the primary analysis in CR/CRh*

rate. If the interim analysis showed statistically efficacious and overall benefit-risk analysis is promising, then the interim analysis will become the primary analysis of this study. In addition, the study will still continue its enrollment until 120 subjects are enrolled and continue to complete the protocol specified procedures.

The interim analysis will be reviewed by an Amgen internal Data Review Team (DRT) including medical scientist, biostatistician, safety scientist, pharmacologist. The interim analysis will be performed by the independent biostatistician and the programmers supporting the DRT. The DRT and independent biostatistician and programmer are independent from the Clinical Study Team, which allows the study integrity to be maintained. The DRT will also review safety data at the time of interim analysis.

Additional ad hoc Interim Analyses may be performed descriptively without alpha spending. Pharmacokinetic samples collected at specific timepoints may be analyzed and reported. The purpose of this analysis is just to provide descriptive analyses of PK, safety, and efficacy information (including 95% confidence intervals) for regulatory submissions and interactions.

8.2 Primary Analysis

Primary analysis will be performed when all enrolled subjects have finished at least 2 cycles of blinatumomab and the safety follow-up visit (if subjects discontinue treatment after 2 cycles) or have discontinued the treatment of blinatumomab and complete the safety follow up visit, whichever occurs first.

8.3 Final Analysis

Final analysis will be performed at the end of the study when all the enrolled subjects have finished all the follow-up visits or have withdrawn from the study, whichever occurs first. The analyses of RFS, OS, alloHSCT rate after achieving CR/CRh*, and safety will be updated.

9. Data Screening and Acceptance

9.1 General Principles

The objective of the data screening is to assess the quantity, quality and statistical characteristics of the data relative to the requirements of the planned analyses. The database will be subject to edit checks outlined in the data management plan by Amgen Clinical Data Management (CDM) department. Any outstanding data issues will be communicated to CDM for resolution before the database is locked.

9.2 Data Handling and Electronic Transfer of Data

The Amgen Global Study Operations-Data Management (GSO-DM) department will provide all data to be used in the planned analyses. This study will use the RAVE database.

9.3 Handling of Missing and Incomplete Data

The descriptive statistics will identify the extent of missing data. Rules for handling missing data related to endpoints are described in the description of analyses ([Section 10](#)). The handling of incomplete and partial dates for adverse events and concomitant medications are described in [Appendix A](#). Handling of missing or incomplete data for exposure-response analysis will be described in the E-R SSAP or associated documents to support population PK/PD dataset generation and E-R analysis.

9.4 Outliers

Any suspected outliers will be investigated by the study team and will be included in the database unless determined to be an error or there is supporting evidence or explanation to justify the exclusion. Any outliers excluded from the analysis will be discussed in the Clinical Study Report (CSR), including the reasons for exclusion and the impact of their exclusion on the study.

9.5 Distributional Characteristics

The statistical assumptions for analysis methods will be assessed. If the assumptions for the distributional characteristics are not met, these will be described and further analyses may be carried out using data transformations or alternative analysis methods. The use of transformations or alternative analysis methods will be justified in the final study report.

9.6 Validation of Statistical Analyses

Programs will be developed and maintained, and output will be verified in accordance with current risk-based quality control procedures.

Tables, figures and listings will be produced with validated standard macro programs where standard macros can produce the specified outputs.

The production environment for statistical analyses consists of Amgen-supported versions of statistical analysis software, for example the SAS System version 9.4 or later. For the exposure–response analysis, refer to the E-R SSAP for software used.

10. Statistical Methods of Analysis

10.1 General Principles

The binomial endpoints including CR/CRh* rate, CR rate, CR/CRh*/CRi rate, alloHSCT rate and MRD response rate will be calculated and the Clopper-Pearson formula ([Clopper and Pearson, 1934](#)) will be used to derive the exact 95% confidence intervals of binomial rates for primary and secondary endpoints. The time-to-event endpoints including RFS and OS will be summarized with hazard ratio, Kaplan-Meier (KM) curves, KM proportions at selected time points, KM quartiles (when estimable), the number of subjects with events, the number of subjects censored, and the pattern of censoring.

Continuous variables will be summarized by the non-missing sample size, mean, standard deviation, median, first and third quartiles, minimum, and maximum.

Categorical variables will be summarized by the percentage in each category.

Subgroup analyses will be performed to explore the consistency of the treatment effect for subgroups described in [Section 7.5](#); this includes:

- Logistic regression for CR/CRh* rate, CR rate, CR/CRh*/CRi rate, alloHSCT rate and MRD response rate, that will estimate the odds ratio and its 95% confidence intervals between subgroups.
- Cox regression for RFS and OS that will estimate the hazard ratio and its 95% confidence intervals between subgroups.

The analyses of biomarker will be separately documented.

10.2 Subject Accountability

The number and percent of subjects who were screened, received protocol-specified therapy along with the reasons for discontinuing protocol-specified therapy and discontinuing study will be summarized. The number and percent of subjects receiving first infusion of blinatumomab will be tabulated. The number and percent of subjects infused will be tabulated by study site. Key study dates for the first subject infused, last subject infused, and data cut-off date for analysis will be presented.

10.3 Important Protocol Deviations

Important Protocol Deviations (IPDs) categories are defined by the study team before the first subject's visit and updated during the IPD reviews throughout the study prior to database lock. These definitions of IPD categories, sub-category codes and descriptions will be used during the course of the study.

Eligibility deviations are defined in the protocol.

10.4 Demographic and Baseline Characteristics

Demographic (ie, age, age group [<35 , ≥ 35 to <55 , ≥ 55], geriatric age group [<65 , ≥ 65 to <75 and ≥ 75] and sex) and baseline disease characteristics will be summarized using descriptive statistics for the Primary Analysis Set. The baseline characteristics to be summarized include:

- B-precursor subtype
- Occurrence and type of any genetic abnormality
- Age at diagnosis
- White blood cell count at diagnosis
- Time to CR following first line treatment
- MRD status following first line treatment
- Relapse/refractory status at baseline
 - Refractory to first line treatment
 - Refractory to salvage therapy
 - In second or greater relapse
 - In relapse after alloHSCT
- Number and type of prior salvage regimens
- Occurrence of prior alloHSCT
- Baseline bone marrow blast count
- Baseline laboratories including: hemoglobin, ANC, leucocytes, platelet counts, and peripheral blasts in blood
- Baseline CD19 status (percentage and absolute number of CD19 positive cells)
- Baseline CD3 status (percentage and absolute number of CD3 positive cells)

10.5 Efficacy Analyses

10.5.1 Analysis of Primary Efficacy Endpoint

The primary efficacy endpoint is the CR/CRh* rate within 2 cycles of treatment with blinatumomab. The response rate will be calculated and the exact binomial 95% confidence interval will be generated for the response rate. Similar analyses will be provided for CR/CRh* rate during the treatment. Subgroup analyses will be performed to explore the consistency of the treatment effect for subgroups described in [Section 7.5](#); this includes a logistic regression that will estimate the odds ratio and its 95% confidence intervals between subgroups. The results will be presented by forest plot.

The primary analysis will be based on the Primary Analysis Set.

10.5.2 Analyses of Secondary Efficacy Endpoints

The secondary efficacy endpoints include relapse-free survival (RFS), CR rate, CR/CRh*/CRi rate, alloHSCT rate, overall survival, MRD response rate, 100 day mortality after alloHSCT, and time to a 10 point decrease from baseline in global health status/Quality of Life (QoL) using the EORTC QLQ-C30.

The CR rate, CR/CRh*/CRi rate, alloHSCT rate and MRD response rate will be calculated and the exact binomial 95% confidence interval will be generated for these response rates.

Subgroup analyses of the CR rate will be performed to explore the consistency of the treatment effect for subgroups described in [Section 7.5](#); this includes a logistic regression that will estimate the odds ratio and its 95% confidence intervals between subgroups. The results will be presented by forest plot. The above subgroup analysis will apply to CR/CRh*/CRi rate, alloHSCT rate and MRD response rate. Subgroup analyses of the RFS and OS will be performed to explore the consistency of the treatment effect for subgroups described in [Section 7.5](#); this includes a Cox regression that will estimate the hazard ratio and its 95% confidence intervals between subgroups. The results will be presented by forest plot.

The 100-day mortality after alloHSCT will be summarized with the 100-day KM rate among the subjects who achieve CR/CRh* and remain in remission without intervening therapy after blinatumomab and undergo alloHSCT.

The RFS time, CR rate, CR/CRh*/CRi rate, MRD response rate, the OS time and the alloHSCT rate will be analyzed based on the Primary Analysis Set. Time to a 10 point decrease from baseline in global health status/Quality of Life (QoL) using the EORTC QLQ-C30 will be performed on the EORTC QLQ-C30 Analysis Set.

10.6 Safety Analyses

10.6.1 Adverse Events

The Medical Dictionary for Regulatory Activities (MedDRA) version 20.0 or later will be used to code all adverse events (AE) to a system organ class and a preferred term. AEs of interest (EOI) categories will be based on search strategies defined by medical coding. Treatment-emergent adverse events are events with an onset after the administration of the first dose of Blinatumomab.

The subject incidence of AEs will be summarized for all treatment-emergent AEs, serious AEs, AEs leading to withdrawal of Blinatumomab, fatal AEs and EOI.

Subject incidence of all treatment-emergent AEs, serious AEs, AEs leading to withdrawal of IP, and fatal AEs will be tabulated by system organ class and preferred term in descending order of frequency; similar summaries will be repeated for EOs. Time to onset of selected EOs (infection, **cytokine release syndrome** and neurologic events) may also be summarized **with descriptive statistics. Duration of selected EOs will be summarized by KM methods and the descriptive statistics for resolved events (number of subjects; number of events; number of days experiencing events: mean, SD, median, Q1, Q3, min, max) and unresolved events (number of subjects, number of events) of selected EOs should also be provided.**

A summary of treatment-emergent AEs will be tabulated by system organ class, preferred term, and worst grade.

Subgroup analyses (if there is a medical or regulatory rationale) will be presented by system organ class and preferred term in descending order of frequency.

The number and percentage of subjects with antibody formation to blinatumomab will be summarized. In addition, changes in vital sign and laboratory parameters will be summarized.

Subject incidence of all disease related events, fatal disease related events, serious disease related events, and disease related events leading to withdrawal from blinatumomab, will also be provided.

Extent of exposure to blinatumomab will be summarized using descriptive statistics. Percentage of subjects and number of cycles with doses held and dose reductions will be calculated.

These analyses will be performed using subjects in the SAS.

10.6.2 Laboratory Test Results

Shift tables between the worst post-baseline and baseline grades for select laboratory parameters defined in [Appendix B](#). Plots or other summaries overtime will be presented for select laboratory parameters including immunoglobulin, platelets, and liver parameters (alanine transaminase, aspartate transaminase, γ -glutamyl transferase, alkaline phosphatase, and total bilirubin) for subjects in the Safety Analysis Set. **The subject incidence of potential cases of Hy's Law will be summarized.**

10.6.3 Vital Signs

The number and percentage of subjects with abnormal changes (defined in [Appendix B](#)) in systolic blood pressure, diastolic blood pressure and heart rate will be summarized for subjects in the Safety Analysis Set.

10.6.4 Antibody Formation

The incidence and percentage of subjects who develop anti blinatumomab antibodies (binding and if positive, neutralizing) at any time will be tabulated.

10.6.5 Exposure to Investigational Product

Descriptive statistics will be produced to describe the exposure to blinatumomab group for subjects in the Safety Analysis Set. The number of cycles of blinatumomab group administered will be summarized with an additional breakdown of the number of cycles completed, discontinued, and re-started. In addition, the duration of therapy, the relative treatment duration, the cumulative dose, and the percent of intended dose will be summarized by cycle and overall. The number and percent of subjects with dose modifications (eg, dose changes, dose interruptions) and reason for modification will be summarized.

10.6.6 Exposure to Other Protocol-specified Treatment

Descriptive statistics will be produced to describe the required pre-medication (dexamethasone) exposure in the Safety Analysis Set.

10.6.7 Exposure to Concomitant Medication

The number and proportion of subjects receiving concomitant medications from study day 1 through safety follow-up will be summarized by preferred term as coded by the World Health Organization Drug (WHO DRUG) dictionary in the Safety Analysis Set. In addition, the number and proportion of subjects receiving anti-cancer therapies during long term follow-up will be summarized by WHO DRUG preferred term in the Full Analysis Set.

10.7 Other Analyses

10.7.1 Pharmacokinetic Analysis

Blinatumomab serum samples will be taken as listed in Schedule of Assessment of the protocol. The Clinical Data Interchange Standards Consortium (CDISC) Analysis Data Model (ADaM) standard will be adopted to create the Analysis Dataset for Pharmacokinetics Concentrations (ADPC). The ADPC dataset includes the following variables: 1) subject level information (eg., subject ID, country, planned treatment, actual

treatment received, population flags); 2) PK variables (eg., concentration, actual and scheduled PK sampling time); 3) Dosing variables (eg., planned and actual dose(s), start time, stop time and duration of drug infusion, time relative to first infusion start); 4) Physical measurement variables (eg., demographics, selected baseline characteristics and laboratory measurements) and 5) Miscellaneous variables (eg., study specific variables).

Pharmacokinetic parameters will be determined with non-compartmental analysis method with PK Analysis Set. PK parameters such as steady state concentration (C_{ss}), volume of distribution, clearance, and elimination half-life will be estimated for subjects who have sufficient evaluable PK data. Summary statistics of PK parameters and data listings of individual blinatumomab concentration data will be provided.

PK data may be subjected to exploratory population PK analysis with an integrated dataset of multiple studies. If the analysis is performed, nonlinear mixed effects modeling will be used. Effect of covariates on exposure will be determined. These may include age, body weight, body surface area, renal function, liver function, and sex. Other covariates may be analyzed if necessary. The results will be reported separately.

Exposure-response relationships for selected efficacy and safety endpoints may be assessed as appropriate. If the analysis is performed, the results will be reported separately.

10.7.2 Analyses of Exploratory Endpoints

Listings and summary statistics of selected CNS events will be generated to explore possible relation with blinatumomab.

For a subgroup of patients, samples for analysis of lymphocyte subsets will be taken at baseline (before first dose on Cycle 1 D1), at cycle 1 (24 hours after the beginning of the infusion [D2] and at the end of the infusion), and at the SFU visit as described in the Schedule of Assessments of the study protocol. If B cells have not recovered (number of CD19-positive cells is 90 to 570 per μL) at the safety follow-up visit lymphocyte subsets will also be collected 6 months (+3 months) after the safety follow-up visit. Analysis will be provided in a Contributing Scientific Report by the Clinical Biomarker and Diagnostics group.

10.7.3 Analyses of Health Related Quality of Life Endpoints

The analyses of health related quality of life endpoints will be described in a SSAP.

10.7.4 Exploratory Biomarker Endpoints Analysis

The investigation of lymphocytes subset, cytokines, and chemokines measurement will be part of a separate biomarker analysis plan by scientists from the Clinical Biomarkers and Diagnostics (CBD) group.

11. Literature Citations / References

Clopper CJ and Pearson ES. The use of confidence or fiducial limits illustrated in the case of the binomial, *Biometrika*. 1934; 26(4):404-413.

12. Appendices

Appendix A. Handling of Dates, Incomplete Dates and Missing Dates for Adverse Events and Concomitant Medications

The following data will be imputed using the following algorithm:

- Adverse Events
- Concomitant Medications

Table 1. Imputation Rules for Partial or Missing Start Dates

Start Date		Stop Date						missing
		Complete: yyyymmdd		Partial: yyyymm		Partial: yyyy		
		< 1 st dose	≥ 1 st dose	< 1 st dose yyyymm	≥ 1 st dose yyyymm	< 1 st dose yyyy	≥ 1 st dose yyyy	
Partial: yyyymm	= 1 st dose yyyymm	2	1	2	1	n/a	1	1
	≠ 1 st dose yyyymm		2		2	2	2	2
Partial: yyyy	= 1 st dose yyyy	3	1	3	1	n/a	1	1
	≠ 1 st dose yyyy		3		3	3	3	3
Missing		4	1	4	1	4	1	1

1 = Impute the date of first dose
 2 = Impute the first of the month
 3 = Impute January 1 of the year
 4 = Impute January 1 of the stop year

Note: If the start date imputation leads to a start date that is after the stop date, then do not impute the start date.

Imputation rules for partial or missing stop dates:

Initial imputation

- For partial stop date mmyyyy, impute the last of the month.
- For partial stop date yyyy, impute December 31 of the year.
- For completely missing stop date, do not impute.
- If the stop date imputation leads to a stop date that is after the death date, then impute the stop date as the death date.
- If the stop date imputation leads to a stop date that is before the start date, then there is a data error and do not impute the stop date. (ie. set the stop date as missing).

Imputation rules for partial or missing death dates:

- If death year and month are available but day is missing:
- If mmyyyy for last contact date = mmyyyy for death date, set death date to the day after the last contact date.
- If mmyyyy for last contact date < mmyyyy for death date, set death date to the first day of the death month.
- If mmyyyy for last contact date > mmyyyy for death date, data error and do not impute.
- If both month and day are missing for death date or a death date is totally missing, **the death date will be imputed as the day after the date last known to be alive.**

Note that the last contact date refers to the last contact (ie, a visit or an assessment) with patient instead of family members. Last contact date would be derived from the latest patient visit/assessment date.

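### SAP Appendix A caps imputed adverse event stop dates at death but not at the data cut-off, and does not say whether imputed dates enter the planned onset and duration summaries

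*SAP*

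**What the plan says.** SAP 9.3 sends partial dates to one place: "The handling of incomplete and partial dates for adverse events and concomitant medications are described in" Appendix A. The appendix opens with "The following data will be imputed using the following algorithm", lists adverse events and concomitant medications, and names no analysis to which the imputed dates are confined.

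- **Start dates (Table 1).** A start that matches the first-dose month or year, or is missing, takes code "1 = Impute the date of first dose" when the stop is missing or not before first dose. Other partial starts take "2 = Impute the first of the month" or "3 = Impute January 1 of the year".
- **Stop dates.** A month-only stop goes to the last day of that month. For a year-only stop: "For partial stop date yyyy, impute December 31 of the year". A completely missing stop is left missing.
- **Upper limit on an imputed stop.** Only one is given: "If the stop date imputation leads to a stop date that is after the death date, then impute the stop date as the death date".

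SAP 10.6.1 says that time to onset of infection, cytokine release syndrome (CRS) and neurologic events may be summarized. It also says that the duration of selected events of interest "will be summarized by KM methods and the descriptive statistics for resolved events", including mean, median and range of days. It gives no date rule of its own. SAP Section 6 limits censoring for OS and RFS to the data cut-off date; adverse event dates have no such limit.

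**The concern.** Two things follow if the rule is applied as written.

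First, an analysis run during follow-up can contain an event marked as resolved on a date that has not yet occurred. The resolution must have been recorded before the data were cut, so such a date is certainly wrong. In a Kaplan-Meier (KM) analysis of duration it becomes an event time beyond any possible observation.

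Second, moving starts back and stops forward gives the widest interval compatible with the partial date. That is cautious for counting events, but for describing how early an event begins and how long it lasts it errs in one direction only. Onset and duration of CRS and neurologic events are important safety descriptions for this product, and under SAP 8.1 the interim analysis may become the primary analysis.

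**Working it through.** The documents give no figure to reproduce here. The check applies the Appendix A rules to dates.

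**1. Overrun past the cut-off.** Overrun = imputed stop minus cut-off. Inputs are the stop rules in Appendix A and assumed cut-off dates.

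| Assumed cut-off | Year-only stop in cut-off year | Month-only stop in cut-off month |
|---|---|---|
| 15 January | 350 days | 16 days |
| 31 March | 275 days | 0 days |
| 30 June | 184 days | 0 days |
| 30 September | 92 days | 0 days |
| 15 December | 16 days | 16 days |

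The largest overruns are 31 − 1 = 30 days (month-only, cut-off on the 1st of a 31-day month) and 365 − 1 = 364 days (year-only, cut-off on 1 January of a non-leap year). With a cap at the cut-off, every entry becomes 0.

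**2. One event through the rules.** Assume first dose on 3 March 2019 and an event with both start and stop recorded only as March 2019. Table 1 gives code 1, so the start is 3 March. The stop rule gives 31 March. Duration = 31 − 3 + 1 = 29 days with onset on day 1, whatever the true values.

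**3. Average overstatement per partly dated stop.** If the true stop is uniform over the unknown period, the mean overstatement is (31 − 1)/2 = 15 days when the day is missing and (365 − 1)/2 = 182 days when month and day are missing.

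**4. Simulation of the rules.** There were 100,000 treatment-emergent events per pattern. Assumptions: first dose uniform over a year, onset uniform over days 1 to 60, and true durations of 1, 2, 3, 5, 7, 10 or 14 days (mean 6.0).

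| Pattern | Mean duration after imputation (days) |
|---|---|
| Complete dates | 6.0 |
| Month-only start | 18.1 |
| Month-only stop | 20.7 |
| Both month-only | 32.9 |
| Year-only start | 33.9 |
| Missing start, complete stop | 35.4 |
| Year-only stop | 187.6 |
| Both year-only | 215.8 |

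Across all 11 partial-date patterns run, no event had an imputed duration shorter than its true one. Mean onset day moved from about 30.5 to about 18.3 (month-only start), 2.6 (year-only start) and 1.0 (missing start).

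**5. Effect on an overall mean.** Overall mean = 6 + f × overstatement, where f is the share of events with a partial stop. The documents do not give f, so a range is shown.

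| f | Month-only stop (+15) | Year-only stop (+182) |
|---|---|---|
| 1% | 6.15 | 7.82 |
| 5% | 6.75 | 15.1 |
| 10% | 7.5 | 24.2 |

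**The case against.** The best defence is that little of this should arise in practice. Protocol 9.2.2.1 lists onset and resolution dates among the attributes the investigator must assign. Protocol 9.2.2.2 requires serious events within 24 hours and follow-up until resolution or stabilization. Section 6.2.2.1 requires hospitalization for at least the first 2 days after treatment start in the first two cycles and after the dose step. Protocol 12.3 and SAP 9.1 provide for queries and resolution of data issues before lock. A CRS event with only a year for its stop would be unusual. The summaries are descriptive, and the bias makes toxicity look longer, so it does not flatter the drug. All of this stands and keeps the point minor. It does not justify a rule that can generate dates after the cut-off.

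A reader might infer more than the documents support:

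- **That the SAP states imputed dates are used in the duration summaries.** It does not. This is inferred from Appendix A being the only rule and carrying no restriction.
- **That durations of CRS, infection and neurologic events are overstated in general.** Complete dates are untouched and completely missing stops are not imputed, so ongoing events are not stretched. The three event types are named only in the optional onset sentence; the duration sentence says only that events are selected.
- **That the wide interval is needed to classify events as treatment-emergent.** SAP Section 6 decides whether an event began before first dose by a CRF flag. Dates matter only for the upper limit of 30 days after the end of blinatumomab.
- **That a partial stop should be treated as censored.** A recorded partial stop means that the event ended. Censoring it would discard that fact and lengthen the KM estimate.

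**Conclusion.** The point holds as a minor one. The missing cap at the data cut-off is a defect on the face of Appendix A: a month-only stop can overrun by up to 30 days and a year-only stop by up to 364. This happens only when the partial stop falls in the cut-off month or year, at an analysis cut within that period.

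The effect on onset and duration summaries rests on the inference that Appendix A dates are used there. For a single partly dated stop it averages about 15 days (month-only) or 182 days (year-only) if true stops are uniform. The effect on the overall summary depends on the share of such events, which the documents do not give and which may be small. No hypothesis test, boundary or efficacy endpoint is affected.

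**What to change.** 1. **Appendix A.** State that every imputed adverse event stop date is capped at the earlier of the death date and the data cut-off date.
2. **Section 10.6.1.** Base the onset summary and the resolved-event duration statistics on events with complete dates, and report how many partly dated events are left out. Show the summary again with imputed, capped dates as a sensitivity. Do not censor events with a recorded partial stop. Events with a complete start and no stop date remain in the KM summary as unresolved.

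The cost is a sentence or two of SAP text and a small programming change. The downside is that a few partly dated events, all known to have resolved, leave the main duration summary; the reported count and the sensitivity summary show how much that matters. The cut-off cap alone has no evident downside.
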